### 15.2.1 Analysis Methods for Secondary Efficacy Endpoints

All secondary endpoint analyses will be performed on the full analysis set.

#### Dichotomized Secondary Efficacy Endpoints

Clinical remission per 9-point modified Mayo score is calculated by using 9-point modified

Document:

\needc-vnasc01\Biosdata\Reistone\SHR0302\CZA55021\Biostatistics

Author:

[REDACTED]

Version Number:

Final v1.2

Version Date:

23Mar2021

Template No: CS\_TP\_BS016 Revision 5

Effective Date: 01Apr2018

Reference: CS\_WI\_BS005

Mayo score where stool frequency subscore  $\leq 1$ , rectal bleeding subscore of 0, and endoscopic subscore  $\leq 1$ . In addition, Clinical remission per total Mayo score is defined as a total Mayo score of 2 points or lower than 2, with no individual subscore exceeding 1 point. The percentage of patients achieve clinical remission per 9-point modified Mayo score or per total Mayo score will be presented at Week 8. The 90% CI for unadjusted rate will be calculated using the Clopper-Pearson method. Adjusted difference between each SHR0302 dose group and placebo group in clinical remission rate and 90% CI will be provided by CMH method after adjusting for prior anti- TNF $\alpha$  treatment/biological treatment. The adjusted effect will be obtained by CMH weighted average of stratum specific rate differences. Stratified Wald confidence interval will be provided [1].

A shift table will be used to evaluate changes from baseline in Stool Frequency, Rectal Bleeding, Endoscopy and Physician's global assessment subscores of total Mayo score and compare these changes of each of the subscores between the treatment arms.

The percentage of patients achieving clinical response or remission (per 9-point modified Mayo score or total Mayo score) and 90% CI will be presented for each treatment group in a figure.

Endoscopy examination will be required at baseline and Week 8 in order to establish Mayo endoscopic subscore.

Endoscopic remission is defined as the findings of colonoscopy subscore of the Mayo score equals 0. The percentage of patients achieve endoscopic remission will be presented at Week 8. Adjusted difference between each SHR0302 dose group and placebo group in endoscopic remission rate and 90% CI will be provided by CMH method after adjusting for prior anti- TNF $\alpha$  treatment/biological treatment. CMH weighted difference in percentages and confidence interval will be caculated [1].

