The efficacy, safety, tolerability, and anti-inflammatory data generated by this proposed phase II study will be essential for evaluating the potential of this promising, novel anti-inflammatory agent as a treatment for moderate to severe active ulcerative colitis so that one or two doses can be selected to progress into further clinical development.

Figure 1: Study Design Diagram

---

Document:

\\\ieedc-vnasc01\Biosdata\Reistone\SHR0302\CZA55021\Biostatistics

Author:

[REDACTED]

Version Number:

[figure not shown]
Final v1.2

Version Date:

23Mar2021

Template No: CS\_TP\_BS016 Revision 5  
Effective Date: 01Apr2018

Reference: CS\_WI\_BS005

The sample size calculation is based on pairwise comparison of clinical response at week 8 among SHR0302 8mg, 4mg BD, 4mg QD dose group and placebo group at the 2-sided 0.1 significance level. 57%, 57%, 50%, 30% clinical response are assumed for 8mg QD, 4mg BD and 4mg QD dose group, placebo group at week 8 respectively. The planned sample size of 35 evaluable patients per treatment group will provide 80% global power to detect at least 1 dose group is different from placebo group by using Hochberg's step-p test. The total sample size is 152 randomized patients with consideration of 8% drop out rate. 152 eligible patients will be randomized to achieve an estimated 140 evaluable patients in the study.

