## 6.6 STATISTICAL TESTS

The default significant level will be 2-sided 0.1; confidence intervals (CI) will be 90% and

Document:

\leedc-vnasc01\Biosdata\Reistone\SHR0302\CZA55021\Biostatistics

Author:

[REDACTED]

Version Number:

Final v1.2

Version Date:

23Mar2021

Template No: CS\_TP\_BS016 Revision 5  
Effective Date: 01Apr2018

Reference: CS\_WI\_BS005

statistical tests will be two-sided, unless otherwise specified in the description of the analyses.

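### The stratified Wald 90% interval for clinical remission differences covers too little when rates are low and unequal, and shrinks to [0, 0] when neither arm has an event

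*SAP*

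**What the plan says.** SAP section 15.2.1 (Dichotomized Secondary Efficacy Endpoints) treats clinical remission in two ways.

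- Rate within one arm: "The 90% CI for unadjusted rate will be calculated using the Clopper-Pearson method". This is an exact small-sample method.
- Difference from placebo: "The adjusted effect will be obtained by CMH weighted average of stratum specific rate differences", followed by "Stratified Wald confidence interval will be provided". This is a large-sample method. No continuity correction, score-type alternative or zero-event rule is given.

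For endoscopic remission the same section promises a CMH-weighted difference and a confidence interval, citing the same reference [1], but does not use the word Wald. It also states: "Endoscopic remission is defined as the findings of colonoscopy subscore of the Mayo score equals 0".

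SAP section 6.6 fixes the general level: "The default significant level will be 2-sided 0.1", with 90% intervals. SAP section 15.2.2 counts a patient with any missing Mayo subscore as a failure. The Hochberg procedure (SAP section 15.1.1) and the sample size (SAP section 3.1) concern clinical response at week 8 only. No remission rate is assumed in either document.

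**The concern.** The Wald variance of a proportion is p(1−p)/n with the observed p. In a cell with no events it is exactly zero, so that cell adds nothing to the standard error. Remission is stricter than response, arms are small, and missing data count as failures, so few events on placebo are plausible. The interval can then be too short. In the extreme case it claims that a difference is known to be exactly zero from about 38 patients per arm.

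What is at stake is the reading of a secondary endpoint. A dose with a small real remission benefit could be shown with an interval that rules that benefit out.

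**Working it through.** **The plan's own figures first.** SAP section 3.1 states that "35 evaluable patients per treatment group will provide 80% global power". Simulating 400,000 trials with 35 per arm, response rates of 57%, 57% and 50% vs 30%, pooled two-proportion z-tests against a shared placebo arm and Hochberg at two-sided 0.10 gives 80.1%, in agreement. The total is "152 randomized patients with consideration of 8% drop out rate". 140/0.92 = 152.2 and 140 × 1.08 = 151.2, so 152 is consistent. Neither figure involves remission.

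**Inputs from the documents.** 152/4 = 38 per arm (1:1:1:1 allocation), two strata (prior anti-TNFα/biological treatment, yes or no), CMH weights, 90% level (z = 1.645).

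**Assumed inputs.** Remission rates are varied over a range. Stratum splits per arm are 34/4, 31/7, 26/12 and 19/19. True rates are the same in both strata. The interval is the standard unpooled form:

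d = Σ w_k (p_1k − p_0k), with w_k proportional to n_1k n_0k/(n_1k + n_0k)

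d ± 1.645 × √( Σ w_k² [p_1k(1−p_1k)/n_1k + p_0k(1−p_0k)/n_0k] )

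**Coverage** by exact binomial enumeration at 38 per arm (nominal 0.90), with the range over the four splits:

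| Active vs placebo | Wald coverage |
|---|---|
| 3% vs 2% | 0.78 |
| 5% vs 2% | 0.83 |
| 10% vs 3% | 0.85–0.86 |
| 15% vs 5% | 0.87–0.88 |
| 20% vs 5% | 0.89 |
| 20% vs 8% | 0.88 |
| 30% vs 10% | 0.88 |
| 57% vs 30% (the SAP's response rates) | 0.88 |
| 2% vs 2% | 0.96 |
| 3% vs 3% | 0.93 |
| 5% vs 5% | 0.89 |
| 10% vs 10% | 0.88 |

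The split changes these entries by less than 0.01. In the wider grid the one visible exception was 8% vs 2%, where coverage ran from 0.84 to 0.88 across splits.

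**Direction of the misses** (nominal 5% on each side, split 31/7). At 10% vs 3% the whole interval lies below the true difference in 11.3% of trials and above it in about 3%. At 5% vs 2% the figures are 14.7% and 2%.

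**Zero width.** With no event in either arm every variance term is zero and the interval is [0, 0]. The probability is (1−p_1)^38 × (1−p_0)^38:

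- 5% vs 2%: 0.95^38 × 0.98^38 = 0.066
- 3% vs 2%: 0.97^38 × 0.98^38 = 0.146
- 2% vs 2%: 0.98^76 = 0.215
- 10% vs 3%: 0.90^38 × 0.97^38 = 0.006

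This also explains the pattern in the table. An interval of [0, 0] is always a miss when the true rates differ and always a hit when they are equal.

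**The alternative.** A stratified Newcombe interval with the same weights covers 0.98 at 3% vs 2% (split 31/7), 0.98–0.99 at 5% vs 2%, 0.94–0.96 at 10% vs 3%, 0.92–0.93 at 15% vs 5% and 0.90 at 30% vs 10%. For 0/38 vs 0/38 the unstratified Newcombe limits are ± z²/(n + z²) = ± 2.706/(38 + 2.706) = ± 6.6 percentage points, in place of [0, 0].

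**The case against.** The case for leaving the text alone has real weight.

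- **Under-coverage is not general.** With equal rates of about 3% or less the Wald interval is conservative. At moderate remission rates the loss is the usual 1 to 2 points at this sample size. A reader might infer that low rates always shorten the interval too far; the table shows otherwise. This stands and limits the point to low, unequal rates.
- **The rates are assumed.** Material loss needs placebo near 2–3% and active no higher than about 10–15%, so a drug with little remission effect. Nothing in the documents says whether that will happen. This stands.
- **Stratification is not the cause.** A reader might blame an empty small stratum, but coverage hardly depends on the split, and no split is given in the documents. Small arms and rare events drive the result.
- **False claims of benefit are scarcely affected.** With equal rates of 2–10% the lower limit exceeds zero in 1.9–6.0% of cases, against a nominal 5%.
- **Dose choice does not hang on these intervals.** A reader might infer that it does. SAP section 3.1 says only that efficacy, safety, tolerability and anti-inflammatory data together serve to select one or two doses, and no rule is tied to a remission interval.
- **Endoscopic remission is less clear.** Wald is not named there, and reference [1] was not available, so a correction described in it cannot be excluded. The subscore-0 definition would make events rarer, but the protocol's endpoint lists (sections 1.4.2 and 7.2.2) use a subscore of at most 1 while its section 7.2.5 uses 0. That conflict is a separate matter.

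What the objection does not answer is the absence of any rule for zero events, and the loss of coverage that the stated method shows when low rates differ.

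**Conclusion.** The point holds in a limited form and is minor. For clinical remission the SAP commits to an interval whose coverage at 38 per arm falls to about 0.83–0.86 when rates are low and unequal (5% vs 2%, 10% vs 3%) and to 0.78 at 3% vs 2%. The misses mostly understate the benefit. A degenerate [0, 0] result has a 6.6% chance per comparison at 5% vs 2%.

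These sizes rest on assumed remission rates, equal rates across strata, and the standard unpooled Wald form. If remission turns out at 20–30% vs 5–10%, little is lost. The intervals are secondary and outside the Hochberg procedure, so the primary conclusion on clinical response does not change.

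**What to change.** In SAP section 15.2.1, keep the CMH-weighted difference as the estimate. Replace the stratified Wald interval for both clinical remission differences (9-point modified and total Mayo score) with a stratified Newcombe or stratified Miettinen-Nurminen 90% interval. Choose one of the two and state it. Name the same method for endoscopic remission, where the text now says only that a confidence interval will be calculated.

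The cost is an edit of a sentence or two and a change of program. Intervals become wider and somewhat conservative when events are very rare: stratified Newcombe covers about 0.94–0.99 in the low, unequal settings above. Data collection, sample size and the primary analysis are untouched.

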1.4.2 Secondary Efficacy Endpoints

- The percentage of subjects that achieve clinical remission per 9-point modified Mayo score at week 8, where stool frequency subscore ≤ 1 , rectal bleeding subscore of 0, and endoscopic subscore ≤ 1
- The percentage of subjects that achieve clinical remission at week 8 as per total Mayo score of 2 points or lower than 2, with no individual subscore exceeding 1 point and a rectal bleeding subscore of 0.
- The percentage of subjects that achieve endoscopic remission (mucosal healing) at week 8, defined by Mayo endoscopic subscore ≤ 1 point.
- Change from baseline in 9 point modified Mayo score at week 8.
- Change from baseline in total Mayo score at week 8.
- Change from baseline in partial Mayo score (Mayo score without endoscopy) at week 1, 4, 8, 9, 12 and 16.
- Change from baseline in the level of biomarkers CRP, faecal calprotectin.
- The systemic exposure of SHR0302 in steady state in Ulcerative Colitis patients (i.e. concentration and area under the curve).

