7.2.2 Secondary Efficacy Endpoints

- The percentage of subjects achieve clinical remission per 9-point modified Mayo score at week 8, where stool frequency subscore ≤ 1 , rectal bleeding subscore of 0, and endoscopic subscore ≤ 1

- The percentage of subjects achieve clinical remission at week 8 as per total Mayo score of 2 points or lower than 2, with no individual subscore exceeding 1 point and a rectal bleeding subscore of 0.
- The percentage of subjects achieve endoscopic remission (mucosal healing) at week 8, defined by Mayo endoscopic subscore \leq 1 point.
- Change from baseline in 9-point modified Mayo score at week 8.
- Change from baseline in total Mayo score at week 8.
- Change from baseline in partial Mayo score (Mayo score without endoscopy) at week 1, 4, 8, 9, 12 and 16.
- Change from baseline in the level of biomarkers CRP, fecal calprotectin.
- The systemic exposure of SHR0302 in steady state in Ulcerative Colitis patients (i.e. concentration and area under the curve).

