7.2.5 Mayo Score Assessment

Mayo score is an instrument designed to measure disease activity of ulcerative colitis. Mayo score ranges from 0 to 12 points. It consists of 4 subscores, each graded from 0 to 3 with higher scores indicating more severe disease (see [Appendix 1](#))

- stool frequency (0-3)
- rectal bleeding (0-3)
- findings of colonoscopy (0-3)
- physician global assessment (PGA) (0-3)

Mayo score is assessed at baseline and Week 8. If the subject scores ≥ 2 on the endoscopic sub-score of the Mayo Score at baseline and meet all other inclusion/exclusion criteria, the subject will be randomized. Should any bowel preparation be required to perform the colonoscopy, 3-day patient diary must be completed and assessed prior to any bowel preparation. For the baseline endoscopy, the duration of the time between endoscopy and baseline should not exceed 10 days. Baseline (Day 0 -Visit 2) endoscopy images/films (eligibility assessment) and Week 8 endoscopy images/films will be submitted to central lab for central reading. The central lab will send eligibility report to confirm eligibility.

The physician global assessment (PGA) acknowledges the three other criteria: the patient's daily recollection of abdominal discomfort and general sense of wellbeing, and other observations, such as physical findings and the patient's performance status.

Clinical response is defined as a decrease from baseline in Mayo score of at least 3 points and at least 30 percent, with an accompanying decrease in the subscore for rectal bleeding of at least 1 point or absolute subscore for rectal bleeding of 0 or 1. Clinical remission is defined as a total Mayo score of 2 points or lower, with no individual subscore exceeding 1 point.

Endoscopic response is defined as decrease from baseline in the findings of the colonoscopy subscore of the Mayo Score ≥ 1 . Endoscopic remission is defined as the findings of colonoscopy subscore of the Mayo score equals 0.

7.2.6 9-point Modified Mayo Score

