### 2.2 SECONDARY OBJECTIVES

The secondary objectives are:

- To evaluate the safety and tolerability of oral SHR0302 in patients with moderate to severe ulcerative colitis.
- To evaluate the efficacy of oral SHR0302 in inducing clinical remission in patients with moderate to severe ulcerative colitis.
- To evaluate the efficacy of oral SHR0302 in inducing mucosal healing in patients with moderate to severe ulcerative colitis.
- To evaluate the change from baseline in the following biomarkers; CRP, fecal calprotectin.

- To further evaluate the efficacy of SHR0302 in maintaining remission.
- To characterize the pharmacokinetics of SHR0302 in moderate to severe active Ulcerative Colitis patients, and explore the correlation of exposure-response.

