## 3.3 CHANGES TO ANALYSIS FROM PROTOCOL

- Two new analysis sets which are all patients enrolled set and all patients randomized set have been added in this SAP. The reason for these changes is to summarize patient disposition clearly.
- In protocol, per protocol set is defined as all patients from FAS who do not have significant protocol violation. Based on the data before the interim database lock, there are some subjects who do not have primary efficacy results at week 8. In order to assess the primary efficacy results based on observed results without non-completers considered failure (NCF) imputation, these subjects without week 8 efficacy results will be excluded from PP set.

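### SAP 15.2.1 redefines endoscopic remission and total-Mayo remission away from the protocol's endpoint lists, without declaring it

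*SAP*

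**What the plan says.** **Endoscopic remission.** Protocol 1.4.2 lists "endoscopic remission (mucosal healing) at week 8, defined by Mayo endoscopic subscore ≤ 1 point". Protocol 7.2.2 lists the same endpoint with the same cut-off. Protocol 7.2.5, which describes the Mayo instrument, requires a subscore of exactly 0. SAP 15.2.1 repeats that 7.2.5 sentence word for word: "Endoscopic remission is defined as the findings of colonoscopy subscore of the Mayo score equals 0".

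**Total-Mayo clinical remission.** Protocol 1.4.2 and 7.2.2 ask for a total of at most 2, "with no individual subscore exceeding 1 point and a rectal bleeding subscore of 0". Protocol 7.2.5 has no bleeding condition: "Clinical remission is defined as a total Mayo score of 2 points or lower, with no individual subscore exceeding 1 point". Nor does SAP 15.2.1: "a total Mayo score of 2 points or lower than 2, with no individual subscore exceeding 1 point".

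**Elsewhere.** SAP 15.2 and protocol 9.3.4.3 name these endpoints without defining them, so a programmer would work from SAP 15.2.1. SAP 3.3 declares two items: "Two new analysis sets which are all patients enrolled set and all patients randomized set have been added in this SAP", and a narrower per-protocol set. SAP 2.2 keeps mucosal healing as an objective.

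**The concern.** The protocol gives each of these two endpoints two incompatible definitions. The SAP adopts the version that differs from the endpoint lists and does not say so. A reader who compares the reported endoscopic remission rate with the protocol's secondary endpoint would take it for a rate of subscore 0 or 1, when it is a rate of subscore 0. Mucosal healing at the listed threshold would have no planned between-group analysis.

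SAP 3.1 says the data will be used to choose one or two doses for further development, and SAP 4.2 plans an unblinded analysis once all patients have had the opportunity to reach week 8. With two definitions in force and no recorded choice, nobody outside the team could tell whether the reported version was settled before or after the results were seen.

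**Working it through.** **Step 1. Is there a planned figure to reproduce?** Not for these endpoints: neither document gives an assumed rate or power for them. The sample-size figures concern the primary endpoint only. Simulating it (35 per arm, response 57/57/50/30%, Hochberg at two-sided 0.1, CMH-type variance) gives 80.1% against the stated 80%. Dropout inflation gives 140/0.92 = 152.2 against 152. Neither depends on the definitions at issue.

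**Step 2. Could a version change explain the mismatch?** The SAP is based on protocol version 3.0. The Amendment 01 text for 1.4.2 and 7.2.2 already contains the rectal bleeding condition, and the itemised changes for Amendments 02 and 03 do not touch these endpoints. So it is not a version effect.

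**Step 3. Endoscopic remission.** Protocol 5.2 admits only patients with endoscopic subscore 2 or 3.

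| Baseline subscore | Fall needed, protocol lists (0 or 1) | Fall needed, SAP (0) |
|---|---|---|
| 2 | at least 1 | 2 |
| 3 | at least 2 | 3 |

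The SAP demands one point more from every patient. Anyone with subscore 1 at week 8 is a success under the lists and a failure under the SAP.

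**Step 4. Total-Mayo remission.** Count the patterns of (stool frequency, rectal bleeding, endoscopy, PGA) with no subscore above 1 and a sum of at most 2:
- SAP: none, one or two of four subscores equal to 1, so 1 + 4 + 6 = 11.
- Protocol lists, bleeding fixed at 0: 1 + 3 + 3 = 7.
- The 4 extra patterns are (0,1,0,0), (0,1,0,1), (0,1,1,0) and (1,1,0,0). All have rectal bleeding 1.

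**Step 5. Consistency between endpoints.** Remission on the 9-point score needs stool frequency at most 1, bleeding 0 and endoscopy at most 1, and is defined alike in both documents. It has 2 × 1 × 2 = 4 patterns.
- In total-Mayo remission but not 9-point remission: 4 of 11 patterns under the SAP, 0 of 7 under the lists.
- In 9-point remission but not endoscopic remission: 2 of 4 under the SAP (those with endoscopy 1), 0 of 4 under the lists.

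These count patterns, not patients.

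**Step 6. Scale per arm.** 152/4 = 38 randomized per arm. One reclassified patient moves an arm's rate by 1/38 = 2.6 points, three by 3/38 = 7.9 and five by 5/38 = 13.2 (patient numbers illustrative). With 35 evaluable patients, one patient is 1/35 = 2.9 points.

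**Step 7. Illustration of precision, on assumed rates.** Suppose 15% on placebo and 40% on an active dose reach subscore 0 or 1. Pairwise power at two-sided 0.1 with 35 per arm is then 77%. If only 25% to 75% of those patients reach 0, with the same fraction in both arms, power is 27% to 62%. With 20% and 40% the figures are 57%, and 20% to 44%.

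**The case against.** The strongest reply is that the SAP invented nothing: both of its definitions stand in current protocol text, so the primary defect is a contradiction inside the protocol, and no section says which passage takes precedence. That is right about the origin. But the two sections headed as secondary endpoints agree with each other, and the SAP follows them for the primary endpoint and for 9-point remission. It leaves them only here. Section 7.2.5 also defines a clinical response of at least 3 points on the total Mayo score, which is no listed endpoint of this trial, so it reads as a description of the instrument. Where a protocol offers two definitions, the choice should be recorded.

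Three further points stand as limits:
- The certain direction applies to each arm's rate. The difference from placebo, which is what SAP 15.2.1 estimates, could grow or shrink.
- A stricter endoscopic endpoint is coherent in itself. The lost nesting in Step 5 shows that the definitions differ; it is not a separate harm.
- These are secondary endpoints of a phase II trial outside the Hochberg procedure, so no error-controlled claim rests on them.

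It can also be said that no data are lost, since shift tables are planned for each subscore. They may show raw counts of endoscopic subscore 0 and 1. They are not planned to give the stratum-adjusted difference and 90% CI for 0 or 1, and tables of separate subscores cannot rebuild the joint total-Mayo criterion.

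**Conclusion.** The concern holds and should be fixed. The SAP's endoscopic remission is strictly narrower, and its total-Mayo remission strictly broader, than the endpoints listed in the protocol, and the choice is undeclared. The conclusion rests on the text alone and needs no assumption about rates. The number of patients reclassified, and the effect on the difference from placebo, cannot be derived from the documents; the power figures in Step 7 hold only for the assumed rates. The primary endpoint, 9-point remission, alpha and sample size are unaffected.

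**What to change.** 1. In SAP 15.2.1, define endoscopic remission (mucosal healing) as an endoscopic subscore of 0 or 1. Define total-Mayo clinical remission as a total of at most 2, no subscore above 1 and rectal bleeding 0. These are the definitions in protocol 1.4.2 and 7.2.2; the sponsor should confirm them.
2. Correct protocol 7.2.5 so that it agrees with the endpoint lists.
3. Record the conflict and its resolution in SAP 3.3.
4. If subscore 0 is also of interest, report it as exploratory under a different name.
5. If treatment codes have already been opened for the week 8 analysis, disclose the correction with its date and report both versions of both endpoints.

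No new data are needed. While blinded, the cost is SAP wording, two derivations, one entry in SAP 3.3 and a clarification of protocol 7.2.5. After unblinding, add the dated disclosure and the duplicate reporting. The documents do not show which case applies.
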